7.4 Missing Dates or Partially Missing Dates

Missing or partially missing dates will be imputed conservatively for concomitant medications, procedures and adverse events (AEs). Specific rules for handling missing or partially missing dates are provided in the Appendix B.

No imputations for other missing safety data will be undertaken.

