8.5 Prior and Concomitant Medications

All prior and concomitant medications will be coded using the current version of the World Health Organization Drug dictionary (WHO Drug Sep2016).

Prior medications are defined as medications with start date before the date of first dose of study medication. Concomitant medications are those taken during the study period, and are defined as medications with start date on or before the date of last dose of study medication and end date on or after the date of first dose of study medication, or no end date.

Prior and concomitant medications will be separately summarized by treatment and overall. Additional summaries will be provided for concomitant medications of interest, including all antihypertensive agents and medications for diabetes mellitus (Type 1 or 2). Summaries will be presented by treatment group and overall.

Listings of all prior and concomitant medications will be provided.

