8.9.2 Secondary Efficacy Analysis

The secondary efficacy endpoint is change from Baseline in AOBP SBP at Week 12 or last available AOBP SBP on or prior to the first date of addition of any new BP medications or increases from any baseline BP medications.

Baseline AOBP is defined as the latest available AOBP on or before the date of first dose date.

Changes/additions to baseline BP medications are recorded on the Antihypertensive Medications eCRF. The earliest date of any recorded increase/addition will be compared to the date of the Week 12 AOBP, and the rules below will be applied. Note that only dates of BP medication increases/additions with start date on or before the upper limit of the Week 12 window will be considered.

- If the earliest date of BP medication increase/addition is on or after the date of the Week 12 AOBP, or there is no record of any increase/addition, the Week 12 AOBP SBP will be used for analysis.
- If the earliest date of BP medication increase/addition is prior to the Week 12 AOBP, or when the Week 12 visit should have occurred if there is no Week 12 AOBP, then the AOBP on or before and closest to the earliest date of change will be used for analysis.
- If a subject has no Week 12 AOBP and no record of any BP medication changes/additions, the subject will not be included in this analysis.

In above rules, the SMBP, if available, may be used in place of a missing AOBP at the same visit.

The secondary efficacy endpoint will be analyzed using an analysis of covariance (ANCOVA) model, with baseline AOBP SBP as a continuous covariate and factors for treatment group, baseline serum potassium (K^+ 4.3 – < 4.7 or 4.7 – 5.1 mEq/L), and Type 1 or 2 diabetes mellitus (Yes or No).

The analysis will be performed using the ITT and PP Populations. A sensitivity analysis will be performed using the last observation carried forward, when a subject has no Week 12 AOBP and no record of any BP medication changes/additions.

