- If the year of the incomplete stop date is **prior to** the year of the last dosing date but is the same as the year of the first dosing date, then the first dosing date will be assigned to the missing date.
- If the year of the incomplete stop date is **after** the year of the last dosing date, then January 1 will be assigned to the missing fields.

Missing day only

- If the month and year of the incomplete stop date are the **same** as the month and year of the last dosing date, then the day of the last dosing date will be assigned to the missing day.
- If either the year of the partial date is **not equal to** the year of the last dosing date or the years of the partial date and the last dosing date are the same but the month of partial date is **not equal to** the month of the last dosing date, then the last day of the month will be assigned to the missing day.

2 Imputation of Dates for Prior/Concomitant Medications/Procedures

Partially missing start/stop dates for prior/concomitant medications and partially missing start dates for prior/concomitant procedures will be imputed in the ADaM dataset for prior/concomitant medications/procedures. However, listings of prior/concomitant medications/procedures data will present the date as is, with missing date components left blank.

For prior/concomitant medications, if the stop date is complete with no missing year, month, or day, and the partially missing start date imputed by the rule below is after the stop date, then the start date will be imputed by the stop date.

Partially missing prior/concomitant medication/procedure start dates will be imputed by the earliest possible date given the non-missing field(s) of the date.

Partially missing prior/concomitant medication stop dates will be imputed by the latest possible date given the non-missing field(s) of the date.

3. Imputation of Dates for Pre-specified Medical History

Partially missing start dates for pre-specified medical history will be imputed in the ADaM dataset for pre-specified medical history. However, listings of pre-specified medical history data will present the date as is, with missing date components left blank.

Partially missing pre-specified medical history start dates will be imputed by the earliest possible date given the non-missing field(s) of the date.

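### Partial start dates for blood pressure drugs added on treatment are set to the earliest possible date, with no floor at first dose, so the secondary SBP rule can select too early a reading, including baseline or screening

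*SAP*

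**What the plan says.** For medications, SAP Appendix B, section 2, reads: "Partially missing prior/concomitant medication/procedure start dates will be imputed by the earliest possible date given the non-missing field(s) of the date". SAP 7.4 sets the scope: "Missing or partially missing dates will be imputed conservatively for concomitant medications, procedures and adverse events (AEs"). SAP 8.5 treats antihypertensives as "concomitant medications of interest, including all antihypertensive agents".

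For the secondary endpoint, SAP 8.9.2 says "Changes/additions to baseline BP medications are recorded on the Antihypertensive Medications eCRF" and then "The earliest date of any recorded increase/addition will be compared to the date of the Week 12 AOBP". If that date falls before the Week 12 AOBP, the outcome is the nearest AOBP on or before it. The only date limit is that "only dates of BP medication increases/additions with start date on or before the upper limit of the Week 12 window will be considered". Baseline is the latest AOBP on or before first dose.

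The adverse event rule in Appendix B, section 1.1, differs: a start date with the day missing in the month of first dose becomes the first dosing date.

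**The concern.** Choosing the earliest possible date is a cautious way to decide whether a drug counts as prior or concomitant. It is not neutral when the same date decides which blood pressure reading becomes a subject's outcome. Moving the start of an added drug backwards moves the selected AOBP backwards too, past the true last reading before the change. It may reach baseline, where the change is zero by construction, or a screening visit.

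The two arms would not be affected equally. Protocol 1.2 expects more placebo subjects to reach the potassium thresholds for stopping spironolactone. Protocol 3.1.2 and Appendix D allow a drug to be added after that at AOBP SBP of 165 mmHg or more. An outcome taken too early would hide rises in SBP mainly on placebo. This is the trial's only secondary endpoint.

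**Working it through.** The documents give no figure to reproduce, so the check applies the rules literally.

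**Inputs**
- Day missing: imputed date = 1st of the known month. Day and month missing: 1 January of the known year (SAP Appendix B, section 2).
- Selected AOBP = latest visit on or before the imputed date (SAP 8.9.2). Change = selected AOBP minus baseline AOBP.
- Nominal visits, in days from first dose: S1 -22, S2 -15, S3 -8, S4/baseline -1, then 7, 14, 21, 28, 42, 56, 70 and 84. Screening visits are taken as 7 days apart (the protocol allows 4 to 10).
- Assumptions: first dose on every calendar date of 2017-2018, and true additions spread evenly over the stated study days.

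**Examples, day missing**

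| First dose | Drug added | Imputed date | AOBP selected | True last AOBP before change |
|---|---|---|---|---|
| 8 March | 29 March | 1 March (7 days before first dose) | S3 (screening) | Week 3 |
| 2 March | 29 March | 1 March (Day 0) | Baseline, change 0 | Week 3 |
| 28 March | 20 April | 1 April (before Week 1) | Baseline, change 0 | Week 3 |

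The third row shows that the imputed date need not precede first dose for baseline to be selected.

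**Enumeration.** Shares are of partially dated additions, not of all subjects.

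| Missing | True addition | Dated before first dose | Screening AOBP | Baseline AOBP | No AOBP available |
|---|---|---|---|---|---|
| Day | Days 8-84 | 11.2% | 10.2% | 8.9% | 0.0% |
| Day | Days 8-29 | 39.2% | 35.8% | 26.3% | 0.1% |
| Day | Days 29-84 | 0.1% | 0.0% | 2.3% | 0.0% |
| Day and month | Days 8-84 | 87.4% | 5.8% | 2.2% | 81.4% |

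With the day missing and additions on Days 8-84, the rule selects the true last pre-change AOBP in only about 21% of cases. In most of the rest it selects a post-baseline reading that is too early.

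**A floor alone.** Flooring the imputed date at first dose, as the adverse event rule does, removes the screening selections but turns them into baseline selections: 10.2% + 8.9% = 19.1% would then have a change of exactly 0.

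**Size per case.** Entry AOBP SBP is at most 160 mmHg. If a drug is added at 165 mmHg or more and baseline is used as the outcome, a rise of at least 165 - 160 = 5 mmHg is recorded as 0. With 280 / 2 = 140 subjects per arm, each such case moves an arm mean by at least 5 / 140 = 0.04 mmHg.

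**The case against.** **The link between the two rules is inferred.** SAP 8.9.2 and Appendix B, section 2, do not refer to each other, and the date imputation is described for the prior/concomitant medication dataset. That is correct. But SAP 7.4 and 8.5 together bring antihypertensives under the rule, and no alternative is stated. A programmer with a partial date would have only Appendix B to follow.

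**Other wording may block the selection.** A drug dated before first dose is hard to call an addition to baseline treatment, and SAP 8.1 requires a post-baseline value where mean change is summarized. Both points have force, but 8.9.2 adopts neither. Applying 8.1 here would drop rescued subjects, which is a different unstated choice.

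**Partial dates may be rare.** Medications are recorded at every visit and incomplete data are queried (Protocol Appendix A and 10.1). This stands, and it limits the size of the point.

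**The bias is conservative.** A pull toward no difference does not favour the superiority claim, and the primary endpoint is untouched. This also stands. It lowers the urgency, but the wrong reading is still selected.

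**Stronger readings a reader might infer.** One is that a date missing both day and month, dated before first dose in 87.4% of cases, is recorded as a change of zero. The documents do not support this: in 81.4% there is no AOBP on or before the imputed date, so the rule yields no value. Another is that each affected subject hides at least 5 mmHg. Appendix D offers its thresholds as recommendations subject to judgment. Increases made for adverse events also trigger the rule with no SBP threshold. A screening value also need not equal baseline, since S2 or S3 may be below 135 mmHg.

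**Conclusion.** The point holds as a minor defect in a stated rule. Read together, Appendix B, section 2, and SAP 8.9.2 can replace the true last pre-change AOBP with an earlier one, and with the day missing they usually do. Baseline or screening values are taken in about 19% of day-missing additions on Days 8-84. These are concentrated on Days 8-29 and nearly absent later. With day and month missing, the rule mostly fails to return a value.

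The direction, toward no difference, rests on additions following raised SBP after spironolactone is stopped, and on this being more common on placebo. The percentages rest on nominal visits, evenly spread additions and an assumed calendar. The effect on the treatment difference cannot be sized, because neither the frequency of partial dates nor the rate of added drugs is given. It is small unless partial dates are common, and nil if the eCRF accepts only full dates. The documents do not support a claim that the secondary result is materially biased.

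**What to change.** Amend SAP 8.9.2 before unblinding:

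- State that Appendix B, section 2, does not set the date of on-treatment antihypertensive additions or increases.
- When such a start date is partial, restrict it to dates that fit the known fields and fall after the last visit at which the drug or dose was not recorded. If the drug or dose was first recorded as started at a visit, use that visit's date. Protocol section 6 has AOBP taken ahead of other procedures (except the questionnaire), so the reading that prompted the change is then kept.
- Consider only increases or additions dated after first dose, and never use a screening AOBP as the outcome.
- State how a subject with no post-baseline AOBP before the change is handled.

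The visit-level medication and AOBP records this needs are already collected. The cost is two or three sentences and a few lines of programming.

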APPENDIX C: LIST OF CENTRAL LABORATORY ASSAYS

| | |
|---------------------------------------|--|
| Serum Chemistry Panel: | Hematology: |
| Alanine aminotransferase | White blood cell count (WBC) |
| Albumin | Red blood cell count |
| Alkaline phosphatase | Hemoglobin |
| Amylase | Hematocrit (Packed Cell Volume) |
| Aspartate aminotransferase | Mean cell volume |
| Bicarbonate | Mean cell hemoglobin |
| Bilirubin (total) | Mean cell hemoglobin concentration |
| Blood Urea Nitrogen | Platelet count |
| Calcium | Differential WBC |
| Creatine kinase | Urine: |
| Creatinine (with eGFR) | Specific gravity |
| Glucose | pH |
| Inorganic phosphate | Protein |
| Iron | Glucose |
| Lactate dehydrogenase | Creatinine |
| Magnesium | Ketones |
| Potassium | Blood |
| Sodium | Urobilinogen |
| Total cholesterol | Leukocytes |
| Total protein | Leukocyte esterase |
| Uric acid | Nitrites |
| Other: | Bilirubin |
| Serum pregnancy | 24-hour urine collection for sodium, creatinine, albumin (for ACR) |
| NT-proBNP | Spot urine for albumin and creatinine (for ACR) |
| Aldosterone and plasma renin activity | Urine pregnancy |
| Spironolactone level | |
